---

## PASS INFORMATION

TITLE	A post-authorisation safety study (PASS) to evaluate the paternal exposure to valproate and the risk of neurodevelopmental disorders including autism spectrum disorder as well as congenital abnormalities in offspring – a population-based retrospective study
PROTOCOL VERSION IDENTIFIER	Version 7.0
DATE OF LAST VERSION OF PROTOCOL	23 January 2023
EU PAS REGISTER NUMBER	EUPAS34201
ACTIVE SUBSTANCE	Antiepileptic drugs (AEDs) including valproate ATC WHO code: N03A
MEDICINAL PRODUCT(S)	Antiepileptic drugs (AEDs) including valproate
PRODUCT REFERENCE	Information is detailed in the cover letter's Annex 1
PROCEDURE NUMBER	EMA/H/A-31/1454
MARKETING AUTHORISATION HOLDER(S) (MAH)	The joint initiative involves several companies via a consortium APOTEX EUROPE B.V.; ARISTO PHARMA GMBH; ARROW GENERIQUES; BETAPHARM ARZNEIMITTEL GMBH; CONSILIENT HEALTH LIMITED; CRESCENT PHARMA; DESITIN ARZNEIMITTEL GMBH; GENERIS FARMACEUTICA S.A.; G.L. PHARMA GMBH; SANDOZ/HEXAL AG; LUPIN; VIATRIS SANTE (LYON): FR; VIATRIS GX BV/SRL: BE; NEURAXPHARM ARZNEIMITTEL GMBH; ORION CORPORATION; SANOFI R&D; STADA ARZNEIMITTEL AG; TECNIFAR S.A.; TEVA PHARMACEUTICALS EUROPE; WOCKHARDT UK LIMITED
JOINT PASS	YES
RESEARCH QUESTION AND OBJECTIVES	
Overall aim
 
The aim of this retrospective cohort study is to examine the association between paternal exposure to valproate at conception and the risk of NDD, including autism spectrum disorders (ASD), as well as congenital malformations (CM) in offspring. Paternal exposure to valproate will be compared to paternal exposure to lamotrigine or levetiracetam.
 
Primary objective
 
 
1. Investigate the risk of NDD, including ASD, in offspring paternally exposed to valproate (monotherapy), compared
 

	
to lamotrigine or levetiracetam (composite monotherapy) treatment at the time of conception.
 
Secondary objectives
 
 
2. Investigate the risk of CM in live and non-live offspring paternally exposed to valproate (monotherapy), compared to lamotrigine or levetiracetam (composite monotherapy) treatment at the time of conception, in Norway and Denmark.
 
3. Describe AED exposure (posology and duration) data and health characteristics of male patients prescribed AEDs (including valproate and lamotrigine/levetiracetam) in treatment of epilepsy and other indications at the time of conception of their offspring, both for NDD and CM cohort.
 
4. Identify potentially important risk factors for outcomes of interest, in offspring paternally exposed to valproate (monotherapy) or lamotrigine or levetiracetam (composite monotherapy) at the time of conception, by examining AED exposure and health characteristics of the offspring and their mothers.
 
 
Exploratory objectives
 
 
5. To describe the putative risk factors and frequency of NDD, including ASD, as well as CM in offspring paternally exposed to valproate (in combination with other AEDs) and to other AEDs (in combination with other AEDs, excluding valproate) at the time of conception.
 
6. To describe the risk factors and frequency of NDD, including ASD, as well as CM in paternally and maternally matched exposure-discordant (valproate vs lamotrigine/levetiracetam monotherapy) siblings at conception.
 
7. To investigate the risk of CM in live offspring paternally exposed to valproate (monotherapy), compared to lamotrigine or levetiracetam (composite monotherapy) treatment at the time of conception in Sweden.
 
8. To describe the frequency of CM by target body system organ class in live and non-live offspring paternally exposed to valproate (monotherapy), and to lamotrigine or levetiracetam (composite monotherapy) treatment at the time of conception.
 

COUNTRY(-IES) OF STUDY
	
The study will be conducted in Denmark, Sweden, and Norway

AUTHOR
	
[name], MPH          [name], MPH          On behalf of IQVIA and the Consortium

## 2. LIST OF ABBREVIATIONS

Abbreviation	Definition
ADHD	Attention-Deficit/Hyperactivity Disorder
AED	Anti-Epileptic Drug
ARND	Alcohol-Related NDD
ASD	Autism Spectrum Disorder
ATC	Anatomical Therapeutic Chemical
CHD	Congenital Heart Defects
CI	Confidence Interval
CM	Congenital Malformations
CoE	Centre of Excellence
CPR	Danish Civil Registration System
DDD	Defined Daily Dose (classification by WHO)
EMA	European Medicines Agency
ENCePP	European Network of Centres for Pharmacoepidemiology and Pharmacovigilance
ERB	Ethics Review Board
EU	European Union
FAS	Foetal Alcohol Syndrome
GVP	Good Pharmacovigilance Practices
HR	Hazards Ratio
ICD-10	International Statistical Classification of Diseases and Related Health Problems 10 th Revision
ICH	International Conference on Harmonisation
IQ	Intelligence Quotient
IQR	InterQuartile Range
ISPE	International Society for Pharmacoepidemiology
IVF	In Vitro Fertilisation
LMP2	Last Menstrual Period + 2 weeks
MAH	Marketing Authorisation Holders
NDD	Neurodevelopmental disorders
NEMEA	Northern Europe, Middle East and Africa
NTD	Neural Tube Defects
OR	Odds Ratio
PAE	Prenatal Alcohol Exposure
PAS	Post-Authorisation Study
PASS	Post-Authorisation Safety Study
PH	Proportional Hazard
PI	Principal Investigator
PRAC	Pharmacovigilance Risk Assessment Committee
PS	Propensity-Score
RWI	Real-World Insight
SAP	Statistical Analysis Plan
SD	Standard Deviation
SES	Socioeconomic Status
SOP	Standard Operating Procedures
SSRIs	Selective Serotonin Reuptake Inhibitors
TS/CT	Tourette Syndrome and Chronic Tic Disorder
WHO	World Health Organization

## 4. ABSTRACT

### Full Study Title

A post-authorisation safety study (PASS) to evaluate the paternal exposure to valproate and the risk of neurodevelopmental disorders including autism spectrum disorder as well as congenital abnormalities in offspring – a population-based retrospective study

### Rationale and background:

Valproate-containing medicines are approved nationally in the European Union for epilepsy and bipolar disorder, and in some countries, for the prevention of migraine. In recent years, due to an increased risk of neurodevelopmental disorders (NDD) including autism spectrum disorders (ASD), and congenital malformations (CM) in offspring after valproate exposure in utero, the use of valproate has been restricted to cases in which no other effective or tolerated treatment is available in women of childbearing potential or in pregnant women suffering from epilepsy; it has been contraindicated in pregnant women suffering from bipolar disorder.

There is currently no real-world evidence of an increased risk of CM and NDD including ASD in offspring following paternal exposure to antiepileptic drugs (AEDs). Therefore, and following the Pharmacovigilance Risk Assessment Committee (PRAC) recommendation dated 08 February 2018, a post-authorisation safety study (PASS) is being conducted to evaluate the association between paternal exposure to valproate and risk of NDD, including ASD, as well as CM in offspring.

### Overall aim

The aim of this retrospective cohort study is to examine the association between paternal exposure to valproate at conception and the risk of NDD, including ASD, as well as CM in offspring. Paternal exposure to valproate will be compared to paternal exposure to lamotrigine or levetiracetam.

### Primary objective

1. Investigate the risk of NDD, including ASD, in offspring paternally exposed to valproate (monotherapy), compared to lamotrigine or levetiracetam (composite monotherapy) treatment at the time of conception.

### Secondary objectives

2. Investigate the risk of CM in live and non-live offspring paternally exposed to valproate (monotherapy), compared to lamotrigine or levetiracetam (composite monotherapy) treatment at the time of conception, in Norway and Denmark.
3. Describe AED exposure (posology and duration) data and health characteristics of male patients prescribed AEDs (including valproate and lamotrigine/levetiracetam) in treatment of epilepsy and other indications at the time of conception of their offspring, both for NDD and CM cohort.
4. Identify potentially important risk factors for outcomes of interest, in offspring paternally exposed to valproate (monotherapy) or lamotrigine or levetiracetam (composite monotherapy) at the time of conception, by examining AED exposure and health characteristics of the offspring and their mothers.

### Exploratory objectives

5. To describe the putative risk factors and frequency of NDD, including ASD, as well as CM in offspring paternally exposed to valproate (in combination with other AEDs) and to other AEDs (in combination with other AEDs, excluding valproate) at the time of conception.

6. To describe the risk factors and frequency of NDD, including ASD, as well as CM in paternally and maternally matched exposure-discordant (valproate vs lamotrigine/levetiracetam monotherapy) siblings at conception.
7. Investigate the risk of CM in live offspring paternally exposed to valproate (monotherapy), compared to lamotrigine or levetiracetam (composite monotherapy) treatment at the time of conception in Sweden.
8. To describe the frequency of CM by target body system organ class in live and non-live offspring paternally exposed to valproate (monotherapy), and to lamotrigine or levetiracetam (composite monotherapy) treatment at the time of conception.

### Study design

This study is a population-based retrospective cohort design using secondary data obtained from national registries. The outcomes of interest in the offspring are NDD including ASD (primary outcome), and a composite of CM (secondary outcome).

For the evaluation of NDD, including ASD, the population for analysis will be comprised of live births for whom medical record linkage to mother and father is available within such registries. For the evaluation of CM, the population for analysis will be comprised of live births, stillbirths and spontaneous abortions during gestation (2nd and 3rd trimester) for whom medical record linkage to mother and father is available within such registries, for Norway and Denmark. For Sweden the corresponding population for analysis will be comprised of live births only. The primary outcome of interest is NDD, including ASD in offspring up to 12 years of age based on ICD-10 diagnostic codes, as recorded in the National Patient Registries. The secondary outcome of interest is a composite of CM diagnosed in offspring up to 12 years of age, stillbirths and spontaneous abortions-based on ICD-10 diagnostic codes, as recorded in the National Patient Registries and Medical Birth Registries. The primary exposure of interest is paternal use of valproate during the spermatogenic risk window prior to conception of the offspring (defined by the first day of the last menstrual period date plus two weeks [LMP2] of the mother within the linked family unit). Exposure information will be derived from prescription data, as recorded in the National Prescription Registries for each country (from 2005 in Sweden, 2008 in Norway and 1995 in Denmark) to 31 December 2018 for Denmark and 31 December 2019 for Sweden and Norway. Country-specific cohorts of eligible linked family units will be identified. These cohorts will be combined (in terms of aggregated results) into an all-Nordic cohort (Sweden, Norway, Denmark for the primary outcome and Norway, Denmark for the secondary outcome) where feasible to further increase validity and statistical power.

### Population:

#### Setting

Subjects for inclusion in the study will be selected from the national registries of Sweden, Denmark, and Norway. These are large, longitudinal patient-level registries that collect secondary data. The study population will comprise live births, stillbirths and spontaneous abortions for whom medical record linkage to mother and father is known within the registries.

In order to perform the data extraction, the following inclusion and exclusion criteria will be applied:

#### Inclusion criteria for data extraction

- Singleton pregnancies, with known pregnancy-length of at least 12 weeks within the study time period;
- Pregnancies linked to both mother and father within the study time period;

 Data about voluntary abortions, that can have a diagnosis of CM, are not linked to fathers in any of the countries at study.

- Father with a continuous enrolment in the database for  $\geq 12$  months prior to linked mother LMP2 date;
- Father with at least one AED in the data available.

For Sweden the inclusion criteria are slightly different, as only live births can be included:

- Singleton pregnancies resulting in live births;
- Pregnancies linked to both mother and father within the study time period;
- Father with a continuous enrolment in the database for  $\geq 12$  months prior to linked mother LMP2 date;
- Father with exposed to at least one AED during 192 days prior to 28 days after LMP2 date

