**Data analysis:**

- Two cohorts will be constructed to evaluate the effect of the paternal valproate exposure on primary and secondary outcomes.
- A STrengthening the Reporting of OBservational studies in Epidemiology (STROBE) diagram will be provided to show cohort exclusions step by step.
- For descriptive analysis of NDD (including ASD), paternal characteristics at conception and maternal characteristics at delivery (index date) will be described overall and by paternal exposure group including demographic and other characteristics such as comorbidities and medication use.
- For descriptive analysis of CM, paternal characteristics at conception and maternal characteristics at the index date (country-specific) will be described overall and by paternal exposure group including demographic and other characteristics such as comorbidities and medication use.
- Demographic and health characteristics of offspring at index date (or during follow-up, as appropriate) will be provided separately for both cohorts, by paternal exposure groups.
- Distribution of the outcomes at study will be presented, separately for each cohort, by paternal exposure group.
- Paternal AED exposure and maternal AED exposure will be characterised by cluster analysis.
- For the primary outcome, a crude and a propensity-score-weighted Cox proportional hazards regression model will be fitted to estimate a hazard ratio (HR) (+ 95% CI) between offspring paternally exposed to valproate and offspring paternally exposed to lamotrigine/levetiracetam (reference group).
- For the primary outcome, the risk and time to onset of NDD will be described by the cumulative incidence (+ 95% CI) of incident events, and cumulative hazard rate (+ 95% CI) of incident events over time. These statistics will be presented for the overall cohort and separately for offspring paternally exposed to valproate or lamotrigine/ levetiracetam (composite and separately).
- For the secondary outcome (country-specific), a crude and a propensity-score-weighted logistic regression model will be fitted to estimate the odds ratio (OR) (+ 95% CI) of CM between

offspring paternally exposed to valproate and offspring paternally exposed to lamotrigine/levetiracetam.

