#### Inclusion criteria for data extraction

- Singleton pregnancies, with known pregnancy-length of at least 12 weeks within the study time period;
- Pregnancies linked to both mother and father within the study time period;
- Father with a continuous enrolment in the database for  $\geq 12$  months prior to linked mother LMP2 date;
- Father with at least one AED in the data available.

For Sweden the inclusion criteria are slightly different, as only live births can be included:

- Singleton pregnancies resulting in live births
- Pregnancies linked to both mother and father within the study time period;
- Father with a continuous enrolment in the database for  $\geq 12$ -months prior to linked mother LMP2 date;
- Father with at least one exposure to AED during 192 days prior to 28 days after LMP2 date

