#### Inclusion criteria for the primary outcome cohort

- Singleton born alive within the study time period (i.e. the birth of only one child during a single delivery)
- Mother with a continuous enrolment for  $\geq 12$ -months prior to child birthdate

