#### 9.7.2.2 *Incidence examination*

The cumulative incidence proportion, rate and time to onset of NDD, including ASD will be calculated as well as cumulative incidence proportion for composite CM endpoint and specific CM target body system organ groups based on ICD-10 codes. These statistics will be presented for each overall cohort and separately for offspring *paternally exposed to valproate or lamotrigine/ levetiracetam (composite and separately) in monotherapy 3 months prior to LMP2*.

The cumulative incidence (risk) of the primary outcomes reported each year will be explored by estimating the cumulative incidence of incident reports (plus 95% CI). For purposes of this analysis the denominator is defined according to the population initially at risk at the beginning of the study, since the estimates are cumulative; that is live births for NDD, including ASD and live plus non-live births for CM. The numerator will comprise of counts of incident events as recorded during each year and summed to reflect the cumulative count for all years up to that point. The cumulative incidence proportion will be calculated according to the formula:

$$\left( \frac{\text{Total number of offspring paternally exposed with newly diagnosed outcome during each cumulative year of interest}}{\text{Population initially at risk}} \right) \times 100$$

For each exposure group, the numerator for each year will contain the number of offspring for whom the incident outcome has been recorded in that year and will exclude offspring who have had an outcome previously, within the study period. The denominator will include offspring within the numerator and also offspring who did not have an outcome recorded in the current year or preceding years (i.e. only the ‘at risk’ population will be considered).

The cumulative incidence rate of the primary outcome will be modelled using survival methods and expressed as number of cases per 1000 patients-years at risk (+95%CI). Data may also be stratified according to other relevant strong risk factors for events of interest (age, gender) and stratum-specific incidence rates examined.

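### In Norway and Denmark the overall-cohort descriptive and incidence rows can include children of fathers on no AED at conception, because the paternal AED criterion has no time limit there

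*Protocol*

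**What the plan says.** Protocol section 9.2.2 (repeated in the abstract, section 4) lists the inclusion criteria for data extraction. The general list, which governs Norway and Denmark, ends with "Father with at least one AED in the data available". A separate Swedish list has "Father with at least one exposure to AED during 192 days prior to 28 days after LMP2 date" in that place. The only explanation offered is "For Sweden the inclusion criteria are slightly different, as only live births can be included".

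Section 9.2.2 then says that the primary and secondary outcome cohorts are formed by further criteria nested within those for extraction. Sections 9.2.2.1 and 9.2.2.2 give these as live singleton birth (primary outcome), maternal enrolment, and no parental history of CM or NDD. None concerns the timing of the father's AED. Further exclusions are announced in the abstract only for the comparative, exploratory and sensitivity analyses.

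Secondary objective 3 is to describe "male patients prescribed AEDs (including valproate and lamotrigine/levetiracetam) in treatment of epilepsy and other indications at the time of conception of their offspring". The abstract's data analysis section says that "paternal characteristics at conception and maternal characteristics at delivery (index date) will be described overall and by paternal exposure group". Section 9.7.2.2 says of the incidence statistics: "These statistics will be presented for each overall cohort and separately for offspring" by paternal monotherapy group.

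**The concern.** A father who received his only AED long before conception, or first received one years after the birth, meets the Norwegian and Danish criterion as written. His child then belongs to the outcome cohort and counts in the overall rows. In Sweden the same child would not be extracted.

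Two things follow for those rows. They do not describe the population that objective 3 names, men on an AED at conception. Entry also depends partly on drug use after follow-up has begun, so the rows condition on the future. A reader who sets the Norwegian, Danish and Swedish overall incidence side by side would be comparing differently selected groups. The stated reason for the Swedish variant, live births only, does not explain why the AED window differs. The limitations in section 9.9.1 mention country differences in variables, coverage and missing data, but not this one.

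**Working it through.** The protocol states no figure to reproduce here. The check is a reading of the criteria plus date arithmetic.

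**Does anything else narrow the criterion?**
- Paternal enrolment (section 9.2.2, with its footnote) requires 12 months before LMP2, but is satisfied by any earlier healthcare contact without later death or emigration. It does not require an AED.
- Sections 9.2.2.1 and 9.2.2.2 add nothing on paternal AED use.
- The 3-month risk window of section 9.3.1 and footnote 10 defines exposure groups. It is not an eligibility rule for the cohorts.
- Section 9.7.3 applies its exclusions to the comparative analyses, not to the descriptive ones in section 9.7.2.

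**How wide is each eligibility window?** The abstract's study design section gives the prescription data as running "from 2005 in Sweden, 2008 in Norway and 1995 in Denmark) to 31 December 2018 for Denmark and 31 December 2019 for Sweden and Norway".
- Sweden: 192 + 28 = 220 days around LMP2.
- Denmark: 1 January 1995 to 31 December 2018 = 8,766 days, or 24.0 years; 8,766 / 220 = 39.8 times the Swedish window.
- Norway: 1 January 2008 to 31 December 2019 = 4,383 days, or 12.0 years; 4,383 / 220 = 19.9 times.

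**How late after birth could a qualifying AED fall?** The study periods are in section 9.2.1.
- Denmark, primary outcome: birth in January 1997, data to December 2018, so about 22 years. Follow-up stops at age 12, so the qualifying AED could come about 22 − 12 = 10 years after the child left observation.
- Norway: birth in January 2010, data to December 2019, so about 10 years.

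These are the limits the wording allows, not typical values.

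**Which results use this population?**
- Affected as written: the overall rows for cohort characteristics (section 9.7.2.1) and for incidence (section 9.7.2.2).
- Not affected: the Cox and logistic models (sections 9.7.3.2.1 and 9.7.3.2.2), which use exposure in the 3 months before LMP2 in every country; the incidence by monotherapy group; and the meta-analysis (section 9.7.6), which combines the two exposure groups only.

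**The case against.** The strongest reply is that an extraction rule is not an analysis population. The line sits under the data extraction heading, and section 9.7.2.1 promises a STROBE diagram of the exclusions that create the cohorts. Sections 9.3.2.3 and 9.7.5 also name a primary outcome cohort for descriptive analyses that the protocol does not define separately, so a tighter definition may exist in the SAP, which is not at hand. The incidence formula in section 9.7.2.2 words its numerator in terms of paternally exposed offspring, which leaves some doubt about who is counted overall. This stands as a caution: that the overall rows hold every eligible child is the plain reading of nested criteria, not an explicit statement. But the protocol does set out cohort eligibility, differently by country, and nothing in it closes the gap.

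It is also fair that no inference rests on the overall rows and that no between-country comparison or pooling of them is planned. Objective 3 is still served by the rows for valproate, lamotrigine and levetiracetam monotherapy.

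A reader might infer that most of the Norwegian and Danish overall cohort was untreated at conception. A steady-state model with one treatment spell of mean length m over T years of data gives a treated share of 1/(1 + T/m). For Denmark (T = 24) that is 8% at m = 2 years and 29% at m = 10, but 45% at m = 20. The documents give no m. The model also counts men, while the unit of analysis is the offspring (section 9.7.1), and it ignores any link between age at treatment and age at fatherhood. It cannot support a statement about the majority.

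**Conclusion.** The point holds for the overall descriptive and incidence rows. Followed as written, Norway and Denmark would report them on cohorts that can include fathers not treated at conception, some selected through use after birth, while Sweden reports them on fathers with an AED around LMP2. This departs from secondary objective 3 and makes the overall rows unlike between countries.

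The size is unknown: the eligibility windows differ by factors of about 40 and 20, but the proportion of offspring affected cannot be obtained from the document. The conclusion assumes that no unseen definition narrows the descriptive cohort.

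A reader might go further and infer that the valproate comparison or the pooled estimates are biased. The documents do not support that, because every such result uses the same 3-month exposure window in all countries. Nor is the Swedish rule itself a strict definition of exposure at conception: it starts well before the 3-month window and runs 28 days past LMP2. The matter is worth correcting because the remedy is cheap, but it touches no effect estimate.

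**What to change.** For the overall tables of characteristics (section 9.7.2.1) and incidence (section 9.7.2.2), restrict all three countries to offspring whose father had AED exposure in the 3-month risk window, determined by the existing footnote 10 rule. Show the number removed, by country, in the planned STROBE diagram.

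Do not write this into sections 9.2.2.1 and 9.2.2.2 as an inclusion criterion for the whole cohort. Sensitivity analysis 1 extends the risk window to 6 months and needs fathers exposed only in the earlier part of it, and the exploratory sibling analysis (section 9.7.4) draws on siblings without paternal valproate exposure. Keep the wider extraction as the source pool for both.

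The cost is a filter on data already held and reissued descriptive tables. Overall counts become smaller in Norway and Denmark, and slightly smaller in Sweden because its 220-day window is wider than the risk window.
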